14. STATISTICAL CONSIDERATIONS

The primary outcomes are late complications following proton beam irradiation to the craniospinal axis and posterior fossa. Late complications are defined as the delayed effects attributable to radiation which occur > 90 days following completion of CSI, while acute effects are those occurring during radiotherapy or up to 90 days after the last dose. Due to a difference

in the CSI dose used for standard-risk and high-risk patients, the two groups will be analyzed separately and thus have separate accrual goals.

14.1 Study Design/Endpoints

Accrual goals are 60 standard-risk and 30 high-risk patients. In the pediatric MB population treated with conventional photon CSI, 3-year progression-free survival of standard-risk patients is in the 75-80% range depending on the concurrent use of chemotherapy, while 65-70% is reported among high-risk patients. Thus, 48 standard-risk and 20 high-risk patients are projected to be evaluable for late complications at 3 years following the CSI completion; patients who progress or die sooner will not contribute in the analysis of late complications.

The primary endpoint of ototoxicity at 3 years following completion of radiation therapy will be based on failure events defined by grade 3 or 4 sensorineural hearing loss (SNHL) according to COG criteria. They include progressive hearing decrease to grade 3 or 4 following mild or moderate loss (grade 1 or 2) typically experienced during platinum-based chemotherapy. All patients who have audiology assessments prior to censorship will contribute to the actuarial analysis. Patients will be censored in the event of death, drop out or progression of disease. The historical rates of late SNHL is in the 50% range among pediatric MB patients [9, 10] treated with conventional CSI and cisplatin-based chemotherapy. We shall conclude proton therapy leads to an improvement in the high-risk group if 7 or fewer of 20 patients were to experience grade 3 or 4 SNHL at 3 years following completion of radiation therapy. The decision rule is associated with 77% power if the SNHL rate were truly reduced to 30% among the high-risk patients. In contrast, the probability is only 13% for concluding incorrectly an improvement if the underlying SNHL rate were 50%. In the null hypothesis for the standard-risk group, we assume conventional CSI and cisplatin-based chemotherapy is associated with an SNHL rate less than 50% due to their lower CSI dose, in particular, 40%. We shall conclude proton therapy leads to an improvement in the standard-risk group if 14 or fewer of 48 patients were to experience grade 3 or 4 SNHL at 3 years following completion of radiation therapy. The decision rule is associated with 80% power if the SNHL rate were truly reduced to 25% among the standard-risk patients. In contrast, the probability is only 8% for concluding incorrectly an improvement if the underlying SNHL rate were 40%.

Published data on neuroendocrine dysfunction and neurocognitive functioning have been based on small sample sizes, varying CSI doses and heterogeneous populations not directly comparable to the pediatric MB and PB patients in this protocol. Therefore, analysis of these endpoints will be focused mainly on estimation and precision. A standard-risk group of 48 patients will provide exact 95% confidence intervals of less than 30% for estimating the rates of neuroendocrine dysfunction and neurocognitive functioning, while the maximum interval width will be 46% based on 20 patients. Confidence intervals will be narrower in the analysis of acute effects, as more patients will be evaluable because very few losses will occur due to progression or death within 90 days following completion of CSI.

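### The 14.1 success rule is a count out of 48 or 20 with no counterpart on the planned actuarial estimate, and its sizing clause on early progressors conflicts with 14.4

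*Combined protocol and SAP*

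**What the plan says.** Section 14.1 plans to enrol 60 standard-risk and 30 high-risk patients. From published progression-free survival (PFS) it concludes that "48 standard-risk and 20 high-risk patients are projected to be evaluable for late complications at 3 years", and adds that "patients who progress or die sooner will not contribute in the analysis of late complications".

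The next paragraph of 14.1 defines the ototoxicity endpoint, grade 3 or 4 sensorineural hearing loss (SNHL), and describes a different handling: "All patients who have audiology assessments prior to censorship will contribute to the actuarial analysis", and "Patients will be censored in the event of death, drop out or progression of disease". Section 14.4 agrees with that paragraph. It bases late-complication incidence on actuarial estimates, mainly at 3 years, and censors patients who die, progress or are lost before then.

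The decision rules are counts. Improvement is concluded for standard risk "if 14 or fewer of 48 patients were to experience grade 3 or 4 SNHL at 3 years" and for high risk "if 7 or fewer of 20 patients were to experience grade 3 or 4 SNHL at 3 years". For standard risk the plan says "the probability is only 8% for concluding incorrectly an improvement if the underlying SNHL rate were 40" per cent, with 80% power at a true rate of 25%. For high risk it gives 13% at a true rate of 50% and 77% power at 30%.

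**The concern.** Two things do not fit together.

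- **Who counts.** Take a child with grade 3 SNHL at 18 months whose tumour progresses at 30 months. Under the sizing clause this child is out of the analysis. Under the endpoint paragraph and 14.4 the child is an event.
- **What is compared with what.** The planned analysis yields a Kaplan-Meier type percentage from about 60 or 30 patients. The decision rule needs a whole number of events out of exactly 48 or 20. No sentence converts one to the other, and none gives a cut-off if the evaluable number differs from 48 or 20.

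This is the only rule by which the trial may conclude that protons reduce hearing loss, and the comparison is single-arm against assumed historical rates of 50% and 40%. If the analysis set and threshold are open, they can be settled after the data are seen, and the stated error rates no longer describe the decision.

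**Working it through.** **1. The plan's own figures.** Inputs from 14.1: n = 48, cut-off 14, rates 40% and 25%; n = 20, cut-off 7, rates 50% and 30%. Formula: P(X ≤ r) = Σ C(n,k) p^k (1−p)^(n−k), summed over k = 0 to r.

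- P(X ≤ 14 | 48, 0.40) = 0.081; P(X ≤ 14 | 48, 0.25) = 0.800.
- P(X ≤ 7 | 20, 0.50) = 0.132; P(X ≤ 7 | 20, 0.30) = 0.772.

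All four stated percentages reproduce.

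**2. How firm are 48 and 20?** The plan says "3-year progression-free survival of standard-risk patients is in the 75-80% range", so 60 × 0.75 = 45 and 60 × 0.80 = 48; the plan uses the top of its range. For high risk the range is 65-70%, so 30 × 0.65 = 19.5 and 30 × 0.70 = 21; 20 lies inside it. Neither figure allows for dropout, although notes 1 and 9 to Table 2 make follow-up visits and follow-up audiograms advisory. If evaluable means progression-free at 3 years, the binomial probability of exactly 48 of 60 is 0.128 at 80% PFS and 0.084 at 75%. For exactly 20 of 30 it is 0.142 at 70%, 0.153 at 66.7% and 0.150 at 65%. Another denominator is therefore the likely case.

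**3. The same count with another denominator** (formula of step 1):

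| Rule | Type I error | Power |
|---|---|---|
| 14 of 45 | 14.3% | 86.7% |
| 14 of 50 | 5.4% | 74.8% |
| 7 of 18 | 24.0% | 85.9% |
| 7 of 21 | 9.5% | 72.3% |

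**4. The rule moved to the actuarial estimate.** A count of 14 or fewer of 48 fits any cut-off from 14/48 = 29.2% to just under 15/48 = 31.25%; the midpoint is 14.5/48 = 30.2%. A count of 7 or fewer of 20 fits 7/20 = 35% to just under 8/20 = 40%; the midpoint is 7.5/20 = 37.5%.

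The estimate is F(3) = 1 − Π(1 − d/n), where d is the number of events and n the number at risk at each event time. It was simulated 40,000 times per scenario with N = 60 and 30. Assumptions that are not in the documents: exponential SNHL onset with hazard −ln(1−p)/3, independent exponential censoring with hazard −ln(PFS)/3, no dropout. PFS was varied over the plan's ranges.

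| Cut-off | Type I error | Power |
|---|---|---|
| Standard risk, 29.2% | 5-6% | 76% |
| Standard risk, 30.2% | 7-8% | 81% |
| Standard risk, just under 31.25% | 10% | 85% |
| High risk, 35% | 7-8% | 71% |
| High risk, 37.5% | 11-12% | 79% |
| High risk, just under 40% | 16-17% | 86% |

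With an assumed 15% dropout by 3 years, the midpoints give about 8-9%/80% and 12-13%/78%.

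**5. What the clause on early progressors changes.** The patients in dispute are those with SNHL before progression. Simulated mean events in all patients minus events in completers:

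- Standard risk, PFS 80%: 21.726 − 19.22 = 2.5 under the null; 13.51 − 11.985 = 1.5 under the alternative.
- High risk, PFS 66.7%: 12.633 − 10.015 = 2.6 and 7.497 − 6.007 = 1.5.

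Across scenarios this is about 1 to 3 patients per group. At the midpoint cut-off, Kaplan-Meier and completers-only reach opposite conclusions in about 4-8% of standard-risk and 7-10% of high-risk trials.

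**The case against.** The strongest reply is that there is only one analysis plan. The troublesome clause ends a sentence that explains how 60 and 30 become 48 and 20. The two passages that describe the analysis, in 14.1 and 14.4, agree on censoring, and a statistician following 14.4 would run Kaplan-Meier. Sizing with a fixed binomial and reporting an actuarial estimate is a common simplification. Objective 1.2.1 is to estimate incidence, and the historical comparators are themselves rounded.

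Most of this stands. The clause is loose sizing language more than a rival plan of equal weight, and the effect at a common cut-off is small. The reply does not supply the missing threshold: whoever follows 14.4 obtains a percentage and finds no rule to apply to it.

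A reader might also infer either of two stronger claims:

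- **That the stated 8%/80% and 13%/77% are miscalculated.** They are not (step 1); they belong to a fixed, fully observed count.
- **That power could be near 63% (standard risk) or 51% (high risk).** Such figures come from applying 14 or fewer to events in all 60 enrolled, or 7 or fewer to events in all 30. No sentence says to do that; the denominators are written as 48 and 20.

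**Conclusion.** The point holds as an incomplete decision rule with one inconsistent clause. The count cannot be applied to the planned estimate, and its stated error rates hold only for exactly 48 or 20 fully observed patients. Depending on which compatible cut-off is later chosen, type I error runs from about 5-6% to 10% (standard risk) and from 7-8% to 16-17% (high risk), with power from 76% to 85% and from 71% to 86%.

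Importance is minor to moderate. The 3-year incidence estimate for objective 1.2.1 is unaffected; only the conclusion of improvement is. The text conflict and the binomial results are certain. The Kaplan-Meier figures are illustrative and rest on independent exponential onset and censoring, with no dropout unless stated.

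**What to change.** 1. In 14.1, change the sizing clause so that patients who progress or die early *will contribute until censored at progression or death*, matching 14.4.
2. Replace the counts with one criterion: *improvement will be concluded if the 3-year actuarial incidence of grade 3-4 SNHL is at most 30.2% (standard risk) or 37.5% (high risk)*. These cut-offs are not in the documents. They are suggested because they nearly reproduce the stated error rates, and the choice is the sponsor's. The literal proportions, 29.2% and 35%, are a stricter option that lowers power to about 76% and 71%.
3. Restate type I error and power for the chosen rule with N = 60 and 30 and an explicit dropout assumption.
4. Record when the cut-off was fixed relative to outcome data. The page date within Section 9.2.3 is 7/20/18 and the test-table notes mention patients enrolled after January 2013, so outcome data may already exist.

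**Cost.** Wording in 14.1 and a short recalculation; no added patients or assessments. At the midpoint cut-offs the stated error rates shift by about 1-2 points.

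Requiring an upper confidence limit below 40% or 50% may look like an equivalent repair, but it is not. At the plan's own success boundary the one-sided 95% exact upper limit is 41.8% for 14/48 and 55.8% for 7/20, so both would fail. In simulation a one-sided 95% limit gives power of about 70-72% and 57-60%, a loss of 80 − 72 = 8 to 80 − 70 = 10 points (standard risk) and 77 − 60 = 17 to 77 − 57 = 20 points (high risk). A two-sided 95% limit costs more.

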14.2 Sample Size/Accrual Rate

Based on recent clinical experience, the protocol is projected to accrue about 18 patients per year combined between the two participating institutions. Enrollment is planned for 5 years in order to meet the overall accrual goal of 90 patients. The observed risk distribution of MB and PB patients has been approximately a 2:1 ratio so that 60 standard-risk and 30 high-risk patients will be accrued for the sample size requirements. A minimum follow up of 3 years is required for observing the late complications of proton beam irradiation.

14.3 Stratification Factors

Enrollment will be stratified by risk group.

14.4 Analysis of Endpoints

Progression-free survival is measured from the start of radiation therapy to the date of documented disease progression or death in the absence of progression. Patients who have not progressed or died will be censored at the time of last follow up. Progression-free survival will be estimated by the Kaplan-Meier method. Acute effects will be summarized according to specific events with exact 95% confidence intervals for binary data. The incidence of late complications will be based on actuarial estimates, primarily at 3 years. Patients who die, progress, or are lost to follow up prior to 3 years will be censored. Other factors which may influence late complications will be explored in multivariate models, including gender, age, radiation dose to the posterior fossa, dose volume histogram of the normal tissue as well as drugs, dosages and sequencing of the chemotherapy regimen. In addition, we shall control for pre-existing hearing deficits in the analysis of ototoxicity, while methotrexate usage will be of interest in the analysis of neurocognitive functioning among high-risk patients. Multivariate analyses will be primarily exploratory due to the modest patient numbers in each risk group.

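### Does the lack of a dating rule for hearing loss in Section 14.4 bias the 3-year SNHL rate?

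*Combined protocol and SAP*

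**What the plan says.** All references are to the combined protocol and SAP.

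- **Estimator (Section 14.4).** "The incidence of late complications will be based on actuarial estimates, primarily at 3 years", with the censoring reasons "Patients who die, progress, or are lost to follow up prior to 3 years will be censored".
- **Hearing endpoint (Section 14.1).** The event is grade 3 or 4 SNHL, counted from the end of radiation. On who contributes: "All patients who have audiology assessments prior to censorship will contribute to the actuarial analysis". On censoring: "Patients will be censored in the event of death, drop out or progression of disease".
- **Decision rules (Section 14.1).** For high-risk patients, the condition for declaring improvement reads "if 7 or fewer of 20 patients were to experience grade 3 or 4 SNHL at 3 years following completion of radiation therapy"; for standard-risk patients, it reads "if 14 or fewer of 48 patients were to experience grade 3 or 4 SNHL at 3 years following completion of radiation therapy". Stated false-positive chances are 13% (at a 50% rate) and 8% (at 40%). The stated power is 77% (at 30%) and 80% (at 25%).
- **Contrast with PFS (Section 14.4).** "Progression-free survival is measured from the start of radiation therapy to the date of documented disease progression or death in the absence of progression", and "Patients who have not progressed or died will be censored at the time of last follow up".
- **Testing schedule (Section 9, Table 2, notes 1 and 9; Section 9.2.2).** Follow-up audiograms are yearly, with a window of six months either side. Extra audiograms before platinum cycles are recommended, and any that are done are added to the data set.

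**The concern.** Hearing loss has no observed onset. It is seen only when an audiogram is done, so its date depends on a convention. Section 14.4 supplies an event date and a censoring date for PFS, a secondary endpoint. For SNHL, a primary one, it gives only an estimator and a list of censoring reasons.

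The year-3 visit window straddles month 36. Suppose an analyst dates loss at the detecting audiogram and reads the curve at month 36. Loss first found after month 36 but within the year-3 window would then be left out of the 3-year rate, although much of it began earlier. The trial has one arm and is judged against fixed rates of 40% and 50%, so no concurrent control would carry the same delay and cancel it. The error would favour declaring improvement. The plan also does not say whether the count of patients or the actuarial estimate settles the rule.

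**Working it through.** **1. The plan's own figures.** With X binomial, the chance of concluding improvement is P(X ≤ r).

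| Group | Rule | At the null rate | At the alternative |
|---|---|---|---|
| Standard-risk | ≤14 of 48 | 8.1% at 40% | 80.0% at 25% |
| High-risk | ≤7 of 20 | 13.2% at 50% | 77.2% at 30% |

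All four agree with Section 14.1.

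**2. The adverse reading.** From the documents: yearly tests, ±6 months, 3-year rates of 40% and 50%. Assumed: visits uniform in the window, all tests done, no censoring, onset F(t) = 1 − (1 − p)^((t/36)^k). Here p is the true 3-year rate, k = 1 is a constant hazard, and smaller k means earlier onset.

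Half the year-3 tests fall in months 30–36. For the other half, the last test before month 36 is the year-2 test, in months 18–30. So

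rate read at month 36 = ½ × mean F over 30–36 + ½ × mean F over 18–30.

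For k = 1:
- p = 40%: ½ × 37.4% + ½ × 28.8% = 33.1%
- p = 50%: ½ × 47.0% + ½ × 36.9% = 41.9%

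For k = 0.25 the same formula gives 38.1% and 47.8%. Hence the ranges 33–38% and 42–48%. Rising hazards widen the gap: k = 2 gives 27.7% and 35.4%.

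**3. The year-3-visit reading.** Same assumptions, with status taken from the test in months 30–42:

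rate = mean F over 30–42.

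For k = 1 this is 39.9% and 49.9%. The binomial false-positive chances are 8.3% and 13.4%, in essence the stated 8% and 13%. Kaplan–Meier simulations with 60 and 30 patients, progression and drop-out gave 39.2–40.1% and 48.8–50.2%.

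**4. Effect on the false-positive chance.** Section 14.4 calls for an actuarial estimate, so the limits are read as proportions: 14/48 = 29.2% and 7/20 = 35.0%.

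| Reading | Standard-risk (stated 8%) | High-risk (stated 13%) |
|---|---|---|
| Detection date, month 36, crude count of 48 or 20 | 13–35% | 18–35% |
| Detection date, month 36, actuarial estimate | 8–29% | 10–26% |
| Nominal visit, actuarial estimate | 5–8% | 8–10% |
| Exact onset times, actuarial estimate | 5–6% | 7–8% |

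The crude count is not the planned analysis. The second row is the relevant one for the adverse reading, and its lower ends do not exceed the stated figures. Nominal dating stays at or below them.

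**5. What the documents already settle.** Death and progression carry their own dates, so the censoring date is open only for patients who are lost or who remain event-free. Censoring those patients at their last audiogram, even with detection dating, gives 35.0–41.2% and 45.0–53.0%, which can lie slightly above the truth. More testing narrows the gap: two audiograms per window give 36.0–38.9% and 45.3–48.8%.

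**6. What is properly left out.** With p = 50% and constant hazard, 8.0% of patients have loss first found in months 36–42, of whom 6.6 points began by month 36. The other 1.4 points (8.0 − 6.6) do not belong in a 3-year rate. Loss found late still enters the 5-year estimate that Section 1.2.1 also asks for.

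**The case for a change.** The strongest case for a change is that detection dating read at month 36 is a common default, nothing in the plan forbids it, and the choice could be made after the data are seen. It could move a primary result by several points. The same paragraph shows that the authors knew how to state event and censoring dates, since they did so for PFS. A few sentences would settle the matter at no clinical cost.

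The gap itself stands: no section names the year-3 audiogram or dates the event. Under the adverse reading with visits uniform in the window, the month-36 rate also read low for every onset pattern tried without progression or drop-out censoring.

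The argument weakens in three places. The adverse reading is one of several, and Section 14.1 words the rules as status at 3 years, which fits the year-3 visit of the study calendar at least as well. The inflated error rates need 40% and 50% to be true month-36 rates, yet the documents give no time point or test schedule for the historical series. If those losses were also dated at detection, some or all of the difference cancels. Finally, a fuller written convention has its own costs. If all year-3 visits ran 0–6 months late, nominal dating would read about 42% for 40% and 53% for 50% (constant hazard). Adjacent windows also share months 30 and 42, and loss already present by day 90 would need its own rule.

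**Conclusion.** No change to the plan follows. Sections 14.1 and 14.4 leave a convention unstated, but they do not state a wrong one. An analyst who takes the audiogram in months 30–42 as the 3-year assessment and applies the 29.2% and 35.0% limits to that estimate recovers rates within about one point of 40% and 50%. The false-positive chance is then no higher than stated, to within rounding.

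The adverse reading would cost about 2–7 points at 40% and 2–8 points at 50%, with actuarial false-positive chances of 8–29% and 10–26%. Those sizes rest on visits uniform in the window, full attendance, a constant or falling onset hazard and historical rates free of detection delay. None of these is in the documents. Later onset or missed audiograms would enlarge the gap, and extra audiograms would shrink it. The favourable result for the year-3-visit reading in turn needs visits roughly symmetric about month 36; if they run late it overcounts slightly, which works against declaring improvement.

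### Late-complication incidence censors death and progression, so the actuarial figure exceeds the proportion of treated children with a complication before progression or death

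*Combined protocol and SAP*

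**What the plan says.** Section 1.2 makes the incidence of ototoxicity, endocrine dysfunction and neurocognitive sequelae the primary objectives, with ototoxicity at 3 and 5 years after radiation. Section 14.4 names the estimator: "The incidence of late complications will be based on actuarial estimates, primarily at 3 years". It then gives the censoring rule: "Patients who die, progress, or are lost to follow up prior to 3 years will be censored". Section 14.1 repeats the rule for the primary hearing-loss endpoint: "Patients will be censored in the event of death, drop out or progression of disease". No cumulative incidence function or other competing-risk method is named anywhere in the document.

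Section 14.1 also supplies the frequency of the censored events, from photon-treated series: "3-year progression-free survival of standard-risk patients is in the 75-80% range depending on the concurrent use of chemotherapy", "while 65-70% is reported among high-risk patients". From these it projects that "48 standard-risk and 20 high-risk patients are projected to be evaluable for late complications at 3 years following the CSI completion", and adds that "patients who progress or die sooner will not contribute in the analysis of late complications". Section 5.5 limits follow-up after progression to survival status, so late effects are no longer assessed from that point.

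**The concern.** When death and progression are censored, 1-KM estimates the risk of a complication in a setting where neither occurs, and it does so only if censored children would have had the same risk as those who remain. I call this the net risk. It differs from the proportion of treated children who are observed to have a complication before they progress or die, which is how a reader would normally understand an incidence in the treated group. Death ends the risk. Progression ends the assessment. Loss to follow-up is ordinary censoring and is not at issue.

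The primary outcomes are descriptive rates, to be read by clinicians and families and set beside historical series. If the figure carries the word incidence without saying which quantity it is, it will be read as the proportion of treated children affected and will be too high for that use. The excess grows with the competing-event rate, so it is larger in high risk than in standard risk.

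**Working it through.** **The plan's own figures.** All come from Section 14.1 and all reproduce.
- Evaluable patients (accrual times 3-year PFS): 60 × 0.75 to 0.80 = 45 to 48 (48 stated); 30 × 0.65 to 0.70 = 19.5 to 21 (20 stated).
- High-risk rule, 7 or fewer of 20: exact binomial probability 0.1316 at 50% and 0.7723 at 30% (13% and 77% stated).
- Standard-risk rule, 14 or fewer of 48: 0.0813 at 40% and 0.8001 at 25% (8% and 80% stated).
- Maximum exact 95% interval widths: 29.5% for n = 48 and 45.6% for n = 20 (under 30% and 46% stated).

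**Inputs for the gap.** PFS at 3 years is 75-80% in standard risk and 65-70% in high risk, so 20-25% and 30-35% progress or die. For the net rates I use the design's null and alternative: 40% and 25% in standard risk, 50% and 30% in high risk.

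**Formula.** Assume constant, independent hazards and one 3-year clock for both processes. With l = −ln(1 − net risk) and c = −ln(PFS), each accumulated over 3 years,

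CIF = l/(l + c) × [1 − exp(−(l + c))].

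Standard risk, net 40%, PFS 80%: l = 0.511, c = 0.223, and 1 − exp(−0.734) = 1 − 0.60 × 0.80 = 0.52. CIF = (0.511/0.734) × 0.52 = 36.2%.

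High risk, net 50%, PFS 70%: l = 0.693, c = 0.357, and 1 − 0.50 × 0.70 = 0.65. CIF = (0.693/1.050) × 0.65 = 42.9%.

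| Group | 1-KM | PFS | CIF | Gap (points) |
|---|---|---|---|---|
| Standard | 25% | 80% | 22.5% | 2.5 |
| Standard | 25% | 75% | 21.9% | 3.1 |
| Standard | 40% | 80% | 36.2% | 3.8 |
| Standard | 40% | 75% | 35.2% | 4.8 |
| High | 30% | 70% | 25.5% | 4.5 |
| High | 30% | 65% | 24.7% | 5.3 |
| High | 50% | 70% | 42.9% | 7.1 |
| High | 50% | 65% | 41.6% | 8.4 |

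**Timing.** If all competing events fall at 3 years, the CIF equals the net risk and the gap is zero. If all fall at the start, CIF = net risk × PFS:
- Standard risk: 25% becomes 18.8-20%, and 40% becomes 30-32%.
- High risk: 30% becomes 19.5-21%, and 50% becomes 32.5-35%.

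**Death alone as the competing event.** The documents do not split PFS failures into deaths and progressions. Assuming 3-year mortality of 5-20%, the gap runs from 0.6 points (net 25%, mortality 5%, CIF 24.4%) to 4.6 points (net 50%, mortality 20%, CIF 45.4%).

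**Check on the progression-free population.** I simulated 400,000 patients per setting, with independent hazards and PFS of 80% or two-thirds. The crude proportions matched the formula to about 0.1 point. Among patients progression-free at 3 years, the proportions with a complication were 25.1%, 39.9%, 29.9% and 50.0%, against net rates of 25%, 40%, 30% and 50%. For that population 1-KM is right.

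**The case against.** The strongest reply is that the plan never sets the crude proportion as its target. Section 14.1 treats children still progression-free at 3 years as the evaluable population, and for them 1-KM is unbiased under independence. That stands, and a reader who infers that every late-complication rate in the trial is biased upward goes too far. But Section 14.1 also lets everyone with audiology before censoring contribute to the actuarial analysis, Section 14.5.1 calls all participants evaluable for toxicity, and Section 1.2 speaks of incidence. The target is left unstated, and the word used suggests the crude quantity.

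Other strong readings are not supported:
- A reader might take the CIF as the proportion of children ever affected. Progression does not prevent hearing or endocrine loss; it only ends its assessment under Section 5.5. The CIF counts complications before progression or death. If later ones counted, the documents do not show which way 1-KM would err.
- A reader might infer a distorted contrast between risk groups. Sections 1.2 and 14 call for separate analyses, and no such contrast is planned.
- A reader might infer that the hearing-loss decisions are compromised. The rules are fixed counts (7 of 20, 14 of 48), and their error rates and power do not depend on the actuarial estimator.
- A reader might want the CIF to replace 1-KM throughout. Section 2.3 describes one benchmark series as a percentage of patients (47.6%) and the other as half of long-term survivors. With no improvement at all (net 50%), the high-risk CIF would be 41.6-42.9%. Against a survivor-based 50%, that would suggest a false proton benefit of 7.1-8.4 points.

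It is also fair to say that the gap is well inside the exact interval widths of about 30% and 46%. It is, however, systematic and would not average out with more patients.

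**Conclusion.** The point holds as one about what the reported figure means, and it deserves a change to the plan. Followed as written, Section 14.4 reports as incidence a number that exceeds the proportion of treated children with a complication before progression or death, by the amounts tabulated above.

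Those sizes rest on historical photon PFS, constant hazards, independence between toxicity and tumour outcome, and progression counted as a competing event alongside death. The direction for this quantity does not depend on the constant-hazard assumption, but the size does, with zero as the lower bound. The documents offer no evidence for or against independence.

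**What to change.** In Section 14.4, with a matching sentence in Section 14.1:
- State the quantity of interest. Report the 3- and 5-year Aalen-Johansen cumulative incidence of each late complication by risk group, with death and progression as competing events and only loss to follow-up censored. Label it *complication before progression or death*.
- Add a sensitivity analysis with death alone as the competing event and progression censored. Only deaths without prior progression count as competing events there.
- Keep 1-KM, labelled as the risk in the absence of progression or death and resting on independence. Use it, and not the CIF, for comparison with survivor-based historical rates.
- Leave the 7/20 and 14/48 rules as they are.

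The cost is plan wording and one standard analysis with its sensitivity version, using dates already collected. No patients, visits or assessments are added. The downside is that two figures must be explained in place of one, and a reader who sets the CIF against a survivor-based benchmark will be misled, so the labels have to appear wherever the numbers do.
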